9.8.1 Drugs to treat anaphylaxis

These include epinephrine 1:1,000, epinephrine 1:10,000, diphenhydramine and methylprednisolone. Epinephrine will be injected parenterally in standard recommended doses. Diphenhydramine will be administered orally or parenterally in doses of 50 mg. Methylprednisolone will be injected intravenously in doses of 10-40 mg as needed to treat anaphylaxis. A kit for anaphylaxis management including required drugs, necessary supplies for airway management and oxygen will be available on-site. The Investigators will be trained and familiarized with common resuscitation procedures. A physician skilled and familiar with emergency cardiac resuscitation will assist on-site at each immunization phase.

9.8.2 Drugs to treat malaria

Chloroquine (CQ) will be the first line drug for malaria treatment. In case of therapeutic failure to CQ, Sulfadoxine-Pyrimethamine (SP) or quinine will be used as recommended by Malian National Malaria Control Program.

10 ADVERSE EVENTS

It is the responsibility of the investigators to document all adverse events according to the detailed guidelines set out below. The participants will be instructed to contact the investigator immediately should they manifest any signs or symptoms that they perceive as serious during the study.

10.1 Eliciting and documenting adverse events

10.1.1 Adverse event definition

An adverse event includes any noxious, pathological or unintended change in anatomical, physiological or metabolic functions as indicated by physical signs, symptoms and/or laboratory detected changes occurring in any phase of the clinical study whether associated with the study vaccine, active comparator or placebo and whether or not considered vaccination related. This includes an exacerbation of pre-existing conditions or events, intercurrent illnesses, or vaccine or drug interaction. Anticipated day-to-day fluctuations of pre-existing conditions that do not represent a clinically significant exacerbation need not be considered adverse events. Discrete episodes of chronic conditions occurring during a study period will be reported as adverse events in order to assess changes in frequency or severity.

Adverse events will be documented in terms of a medical diagnosis. When this is not possible, the adverse event will be documented in terms of signs and/or symptoms observed by the investigator or reported by the subject at each study visit.

Pre-existing conditions or signs and/or symptoms (including any which are not recognized at study entry but are recognized during the study period) present in a participant prior to the start of the study will be recorded on the Medical History form within the participant's CRF. Any of the signs or symptoms to be solicited present during physical examination of the participant at each vaccination visit will be recorded on the Prevaccination assessment page of the participant's CRF.

Adverse events, which occur after informed study consent is obtained, but prior to vaccination, will be documented in the Medical History form within the subject's CRF

Any hospitalization will be considered a serious adverse event. However, hospitalization for either 1) elective surgery related to a pre-existing condition that did not increase in severity or frequency following initiation of the study, or 2) for routine clinical procedures that are not the result of an adverse event, need not be considered as adverse events and are therefore not serious adverse events. (See section 10.5).

Adverse events to be recorded as endpoints are described in Section 10.1.4 All other adverse events will be recorded as unsolicited adverse events.

10.1.2 Surveillance period for occurrence of adverse events

All adverse events occurring within 31 days following administration of each dose of vaccine must be recorded on the Adverse Event form in the participant's CRF, irrespective of severity or whether or not they are considered vaccination-related.

Solicited adverse events will be elicited for an 8-day follow-up period (day of vaccination and days 1, 2, 3 and 7 after vaccination) and unsolicited adverse events will be recorded during a 31-day follow-up period (day of vaccination and 30 subsequent days). Serious adverse events will be recorded throughout the study.

Instances of death, cancer or congenital abnormality in offspring of a study subject if brought to the attention of the investigator AT ANY TIME after cessation of study AND suspected by the investigator to be related to study vaccine, will be reported to the sponsors and GSK Biologicals.

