6 STUDY DESIGN AND METHODOLOGY

6.1 Overview

- Double blind, randomized controlled phase I study
- One study center
- Screening will be done within 35 days prior to the first immunization
- 40 adults will be randomized in a 1:1 ratio to receive either FMP1/AS02A or Imovax® Rabies vaccine
- Immunization schedule will be on study days 0, 30 ± 7 , and 60 ± 7
- Route of immunization will be deltoid muscle IM
- Data will be collected onto source records and transcribed onto CRFs
- Study duration will be approximately 12 months per participant
- 8-day follow-up (day of vaccination and days 1, 2, 3 and 7 after vaccination) of solicited adverse events
- 31-day follow-up (day of vaccination and 30 subsequent days) of unsolicited adverse events
- Follow-up of serious adverse events (SAEs) until resolution
- Beginning Study Day 120, participants will be visited and assessed by local guides at home at monthly intervals and will be asked to return to clinic every 3 months for safety follow-up.

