| Urine β-HCG | ● ^a | ● ^b | | | ● ^b | | | ● ^b | | | ٠ | ● ^d |
| CBC | ● ^a | ● ^c | | ٠ | • ^c | | ٠ | • ^c | | ٠ | ٠ | ● ^d |
| Serum chemistry (Creatinine, ALT) | ● ^a | •° | | ٠ | • ^c | | ٠ | • ^c | | ٠ | ٠ | ● ^d |
| Serum for anti-MSP1 response | | •° | | ٠ | •° | | ٠ | • ^c | | ٠ | ٠ | ● ^e |
| Monthly home visit by local guides | | | | | | | | | | | | • ^h |
| Review of health status | | | | | | | | | | | | ● ⁱ |
| Scheduled blood volume (ml) | 5-10 | 5- 10 | 0 | 5- 10 | 5- 10 | 0 | 5- 10 | 5- 10 | 0 | 5- 10 | 5- 10 | 15-30 |
| Cumulative Blood Volume (ml) | 5-10 | 10- 20 | 10- 20 | 15- 30 | 20- 40 | 20-40 | 25- 50 | 30- 60 | 30-60 | 35- 70 | 40- 80 | 55-110 |

a. Performed within 35 days prior to immunization

b. Performed just prior to each immunization

c. Blood collected just prior to each immunization

d. CBC, creatinine, ALT and urine β-HCG will be determined every 3 months from study Day 180 through study Day 364

e. Serum for MSP1 antibodies collected every 3 months from study Day 180 through study Day 364

f. Pre-dose and 30mn after each dose

g. Performed each time symptoms/signs evoking clinical malaria are present

h. Monthly local guides home visits to check the status of participants starting from study Day 120

i. Record any new onset chronic or acute diseases or other medically significant conditions, unscheduled clinic visits and any new treatments since previous scheduled study visit.

Table 2: Intervals between study visits

| Interval | Size of interval in days |
|---------------------------------|--------------------------|
| Visit $2 \rightarrow Visit 7$ | 14 ± 3 |
| Visit $2 \rightarrow Visit 8$ | 30 ± 7 |
| Visit $8 \rightarrow Visit 13$ | 14 ± 3 |
| Visit $8 \rightarrow Visit 14$ | 30 ± 7 |
| Visit $14 \rightarrow Visit 19$ | 14 ± 3 |
| Visit $14 \rightarrow Visit 20$ | 30 ± 7 |

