10.1.3 Recording adverse events

At each visit/assessment, the investigator will evaluate all adverse events either observed by the investigators or reported by the participant spontaneously or in response to a direct question. New adverse events will be recorded in the Adverse Event form within the participant's CRF. The nature of each event, date and time (where appropriate) of onset, outcome, intensity and relationship to vaccination will be established. Details of any corrective treatment will be recorded on the appropriate page of the CRF. See Section 10.5 for instructions for reporting and recording of serious adverse events.

As a consistent method of soliciting adverse events, the participant will be asked a non-leading question such as: "Have you felt different in any way since receiving the vaccine or since the last visit?" The investigator will record only those adverse events having occurred within the time frames defined above.

Adverse events already documented in the CRF, *i.e.* at a previous assessment and designated as 'ongoing' will be reviewed at subsequent visits, as necessary. If these have resolved, the documentation in the CRF will be completed. If an adverse event changes in frequency or intensity during a study period, a new record of the event will be started.

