10.1.5 Unsolicited adverse events

Unsolicited adverse events will be recorded in dedicated space within the CRF. Unsolicited adverse events are adverse events reported by the participants that are different from those solicited or solicited symptoms that begin after the 8-day follow-up period for solicited adverse events. Should any systemic (general) signs/symptoms be reported, their relationship with the study vaccine will be assessed by the investigators and transcribed into the CRF, as descried in section 10.3.

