12.5.3 Analysis of safety

The overall percentage of participants with at least one local adverse event (solicited and unsolicited) and the percentage with at least one general adverse event (solicited and unsolicited) during the 8-day follow-up period after vaccination will be tabulated. The incidence, intensity and relationship of individual solicited symptoms over the 8-day follow-up period will be calculated per group and vaccine dose.

The number of participants with at least one report of an unsolicited adverse event, classified by WHO-preferred terms, reported up to 30 days after vaccination will be tabulated per group and vaccine dose. The intensity and relationship to vaccination of the unsolicited symptoms reported will also be assessed.

Serious adverse events are expected to be rare, but where observed will be described. Comparisons of incidence of symptoms, local and general symptoms will be made based on a two-tailed Fischer exact test. Analysis of safety during the 12-month follow-up period will consist of comparison of incidence of serious adverse events as well as hemoglobin, creatinine and ALT levels.

Clinical laboratory parameters

Hematological (CBC) and biochemical (ALT, creatinine) laboratory parameters will be measured at specific time points, Days 0, 14, 30, 44, 60, 74, 90 and starting on day 180 every 3 months. Clinically relevant abnormal values will be tabulated and a trend analysis could be performed if deemed necessary.

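### The 31-day unsolicited-event window does not fit the visit schedule: the last recording visit can precede the end of dose 3's window, and recording between late doses is contradictory

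*Protocol*

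**What the plan says.** Section 10.1.2 fixes the window: "unsolicited adverse events will be recorded during a 31-day follow-up period (day of vaccination and 30 subsequent days"). The same section also says, more loosely, "All adverse events occurring within 31 days following administration of each dose of vaccine must be recorded on the Adverse Event form". The Summary lists unsolicited symptoms after each vaccination as a co-primary endpoint, and section 12.5.3 counts participants with at least one unsolicited event "reported up to 30 days after vaccination will be tabulated per group and vaccine dose".

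On dosing, section 6.1 says "Immunization schedule will be on study days 0, 30 ± 7 , and 60 ± 7". Table 2 sets 30 ± 7 days from Visit 2 to Visit 8 (dose 1 to dose 2) and again from Visit 8 to Visit 14 (dose 2 to dose 3).

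On recording, section 10.1.3 says "The investigator will record only those adverse events having occurred within the time frames defined above". Yet at Visits 8 and 14 section 7.1.5 has staff record, before the injection, every unsolicited event since the previous visit, with no Day 30 cut-off.

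For the last dose, section 7.1.3 and Table 2 place Visit 20 at 30 ± 7 days after dose 3, while section 7.1.5 places it at study Day 90 ± 10. The schedule of procedures asks for unsolicited events over a minimum of 30 days after vaccination. It marks that row up to Day 90 and leaves it blank for Days 120 to 364. The next clinic visit is Day 180 ± 14.

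**The concern.** A per-dose safety endpoint needs three things: observation through the whole window, one clear rule on what is recorded, and windows that can be told apart. On a literal reading, the schedule can fail on each.

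The first two matter more because they concern data collection. An analysis plan can allocate events that were recorded; it cannot recover events that nobody asked about or that staff were told not to write down. The third is a matter of tabulation. With 20 participants per group, moving one participant from one dose's row to another changes a per-dose rate by 1/20, or 5 percentage points.

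**Working it through.** **Inputs.** Window: the day of vaccination plus 30 days (section 10.1.2). Interval between doses, d: 30 ± 7, so 23 to 37 days (Table 2). Dose 3: study Day 60 ± 7, so Days 53 to 67 (section 6.1). Visit 20: 30 ± 7 days after dose 3 (section 7.1.3, Table 2), or study Day 90 ± 10, so Days 80 to 100 (section 7.1.5).

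**The plan's own figure.** 1 + 30 = 31 days, numbered 0 to 30. This reproduces the stated 31 days.

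**End of dose 3's window.**
- Section 7.1.3 and Table 2: earliest Visit 20 is 30 − 7 = 23 days after dose 3. Post-dose days 24 to 30 remain, which is 7 days.
- Section 7.1.5 read alone: the latest dose 3 is Day 67 and the earliest Visit 20 is Day 80, so 80 − 67 = 13 days. Post-dose days 14 to 30 remain, which is 17 days. At the other extreme, 100 − 53 = 47 days.
- Example: dose 3 on Day 60 and Visit 20 on Day 83. The window ends on Day 90. The next clinic visit is between Day 166 and Day 194, that is 83 to 111 days after Visit 20.

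**Windows between doses.** Overlap = max(0, 31 − d); days in no window = max(0, d − 31).

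| Days to next dose (d) | Overlap (days) | Days in no window |
|---|---|---|
| 23 | 8 | 0 |
| 29 | 2 | 0 |
| 30 (on time) | 1 | 0 |
| 31 | 0 | 0 |
| 32 | 0 | 1 |
| 37 | 0 | 6 (Days 31 to 36) |

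There are 37 − 23 + 1 = 15 permitted intervals: 8 overlap (23 to 30), 1 fits exactly (31) and 6 leave days outside any window (32 to 37). With all three doses on time, 3 × 31 = 93 dose-days cover 91 distinct days (Days 0 to 90); Days 30 and 60 are shared. If the looser wording in section 10.1.2 is read as Days 0 to 31, the overlap is 2 days on time and 9 at d = 23, and 5 days are uncovered at d = 37.

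**Recording rules side by side.** Take d = 37 and an event starting on Day 33. It lies in neither dose 1's nor dose 2's window, so section 10.1.3 says not to record it. Visit 8 in section 7.1.5 says to record it, because it began since the previous visit. Staff cannot follow both.

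**The case against.** The strongest reply is that much of this belongs in an analysis plan. The protocol provides for a Report and Analysis Plan, which is not shown. Onset date, and time where appropriate, is collected, so events can be assigned to a dose later. This stands: a reader might infer that the protocol double-counts events, but no text says so, and the missing attribution rule is not in itself an error.

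A reader might also infer from section 10.1.5, which classes as unsolicited "solicited symptoms that begin after the 8-day follow-up period for solicited adverse events", that a headache just after an early dose 2 is both a solicited event of dose 2 and an unsolicited event of dose 1. Section 10.1.1 points the other way: unsolicited events are those other than the solicited ones. The wording is open, but dual classification is not established.

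On schedule, the overlap is only the vaccination day, and section 7.1.5 separates events recorded before the injection from those after it. An overlap of 15 days, from dose 2 on Day 37 and dose 3 on Day 53, would need a 16-day interval, which Table 2 excludes.

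There is also some later capture. Guides visit homes monthly from Day 120, participants may attend the clinic when sick, a later health-status review asks about new conditions since the previous scheduled visit, and serious adverse events are recorded throughout. For non-serious events this is partial and relies on recall weeks later. The guides' described task in section 7.1.5 is to confirm location and remind participants of visits, although section 6.1 says that they also assess them.

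None of this removes the conflict between sections 10.1.3 and 7.1.5, or a final recording visit that may come before the window closes.

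**Conclusion.** The point holds at moderate severity. Followed as written, the protocol allows the last unsolicited-event visit at 23 days after dose 3, leaving up to 7 of 31 days of a co-primary window without a scheduled clinic assessment until about Day 180. The figure of 17 days applies only if section 7.1.5 is read without section 7.1.3 and Table 2; its main value is to show that the Visit 20 windows conflict. For doses 32 to 37 days apart, 1 to 6 days lie in no window and the recording instructions contradict each other. For doses 23 to 30 days apart, windows overlap by 8 down to 1 days and can blur per-dose rates if no attribution rule is set.

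A reader might go further and infer bias against the more reactogenic vaccine. The documents do not support that: the windows are the same in both groups, and no reactogenicity rates by group are given from which to size such an effect. A count of participants with any unsolicited event over the whole vaccination period would not be affected by the overlap. These figures are limits of the permitted windows, not forecasts; how many participants would be seen early or late is unknown.

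**What to change.** 1. In section 10.1.2, require continuous recording of unsolicited events from dose 1 to 30 days after dose 3, state the window in one way only, and align section 10.1.3 with section 7.1.5.
2. Reconcile the Visit 20 windows in sections 7.1.3 and 7.1.5 and Table 2 so that the final unsolicited-event assessment is no earlier than 30 days after dose 3.
3. In section 12.5.3, assign each event by onset date and time to the most recent dose, and say whether events after post-dose day 30 but before a late next dose enter the per-dose table or are listed separately. In section 10.1.5, say that an event inside any dose's 8-day solicited period is not also an unsolicited event of an earlier dose.

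The cost is wording and one visit window, with no added participants or blood draws. If the upper limit of 37 days is kept, Visit 20 would have a range of 30 to 37 days after dose 3 in place of 23 to 37, which is tighter to schedule. Assigning events to the most recent dose shortens the dose 1 and dose 2 windows by up to 31 − 23 = 8 days when the next dose is early, so the per-dose tables should show the days observed. Items 1 and 2 need to be settled before vaccination starts, because unrecorded events cannot be reconstructed; item 3 can go in the analysis plan.

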10.1.3 Recording adverse events

At each visit/assessment, the investigator will evaluate all adverse events either observed by the investigators or reported by the participant spontaneously or in response to a direct question. New adverse events will be recorded in the Adverse Event form within the participant's CRF. The nature of each event, date and time (where appropriate) of onset, outcome, intensity and relationship to vaccination will be established. Details of any corrective treatment will be recorded on the appropriate page of the CRF. See Section 10.5 for instructions for reporting and recording of serious adverse events.

As a consistent method of soliciting adverse events, the participant will be asked a non-leading question such as: "Have you felt different in any way since receiving the vaccine or since the last visit?" The investigator will record only those adverse events having occurred within the time frames defined above.

Adverse events already documented in the CRF, *i.e.* at a previous assessment and designated as 'ongoing' will be reviewed at subsequent visits, as necessary. If these have resolved, the documentation in the CRF will be completed. If an adverse event changes in frequency or intensity during a study period, a new record of the event will be started.

10.1.4 Solicited adverse events

Local (injection site) adverse events

Pain at injection site Swelling at injection site Erythema Limitation of arm motion (abduction at the shoulder)

General adverse events

Fever (oral body temperature ≥ 37.5°C) Chills Nausea Headache Malaise Myalgia Joint pain Temperature will be recorded at the time of the clinic visit. If additional temperature measurements are recorded at another time of the day, the highest temperature will be recorded.

The assessment of severity/intensity will be as described in Section 10.2. For general signs and symptoms reported, the investigators will assign causality as described in Section 10.3 For all signs and symptoms reported, the investigators will report the outcome as described in Section 10.4.

10.1.5 Unsolicited adverse events

Unsolicited adverse events will be recorded in dedicated space within the CRF. Unsolicited adverse events are adverse events reported by the participants that are different from those solicited or solicited symptoms that begin after the 8-day follow-up period for solicited adverse events. Should any systemic (general) signs/symptoms be reported, their relationship with the study vaccine will be assessed by the investigators and transcribed into the CRF, as descried in section 10.3.

10.2 Assessment of intensity

For each solicited symptom the participants will be asked if they sought medical advice for this symptom.

For all other adverse events than those in Table 3, maximum intensity will be assigned to one of the following categories:

0 = No adverse event

1 = An adverse event which is easily tolerated by the subject, causing minimal discomfort and not interfering with everyday activities.

2 = An adverse event that is sufficiently discomforting to interfere with normal everyday activities.

3 = An adverse event that prevents normal, everyday activities. Such an adverse event would for example prevent attendance at work/school and would require the administration of corrective therapy.

Intensity of the following adverse events will be assessed as described in Table 3:

Table 3: Assessment of adverse event intensity

Version 19, DEAP/MRTC/MMVDU CONFIDENTIAL

| Adverse Event | Intensity grade | Intensity definition | |
|----------------------------|-----------------|--|--|
| Pain at injection site | 0 | None | |
| - | 1 | Pain that is easily tolerated | |
| | 2 | Pain that interferes with daily activity | |
| | 3 | Pain that prevents daily activity | |
| Swelling at injection site | 0 | 0 mm | |
| Record size | 1 | $>0 - \le 20 \text{ mm}$ | |
| | 2 | $>20 - \le 50 \text{ mm}$ | |
| | 3 | >50 mm | |
| Erythema at injection site | 0 | 0 mm | |
| Record size | 1 | $>0 - \le 20 \text{ mm}$ | |
| | 2 | $>20 - \le 50 \text{ mm}$ | |
| | 3 | >50 mm | |
| Limitation of arm motion - | 0 | None | |
| Abduction at the shoulder | 1 | >90° but <120° | |
| | 2 | >30° but ≤90° | |
| | 3 | ≤30° | |
| Fever | 0 | <37.5°C | |
| Record oral temperature | 1 | 37.5 - ≤38.0°C | |
| | 2 | >38.0 - ≤39°C | |
| | 3 | >39°C | |
| Chills | 0 | None | |
| | 1 | Chills that are easily tolerated | |
| | 2 | Chills that interfere with daily activity | |
| | 3 | Chills that prevent daily activity | |
| Nausea | 0 | None | |
| | 1 | Nausea that is easily tolerated | |
| | 2 | Nausea that interferes with daily activity | |
| | 3 | Nausea that prevents daily activity | |
| Headache | 0 | None | |
| | 1 | Headache that is easily tolerated | |
| | 2 | Headache that interferes with daily activity | |
| | 3 | Headache that prevents daily activity | |
| Malaise | 0 | None | |
| | 1 | Malaise that is easily tolerated | |
| | 2 | Malaise that interferes with daily activity | |
| | 3 | Malaise that prevents daily activity | |
| Myalgia | 0 | None | |
| | 1 | Myalgia that is easily tolerated | |
| | 2 | Myalgia that interferes with daily activity | |
| | 3 | Myalgia that prevents daily activity | |
| Joint pain | 0 | None | |
| | 1 | Joint pain that is easily tolerated | |
| | 2 | Joint pain that interferes with daily activity | |
| | 3 | Joint pain that prevents daily activity | |

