The largest clinical experience thus far has been in Gambian adults, in a series of Phase 1 and 2b studies in which seven hundred and eleven doses of RTS,S/AS02 were A pooled analysis of the reactogenicity showed that headache (34%) and administered. malaise (25%) were the most frequently reported general symptoms. There were 4 reports of a general symptoms of maximum intensity (grade 3) probably or suspected to be related to vaccination in this population. All were reported in a phase 2b efficacy study after administration of a 4th dose booster vaccination: 1 case of arthralgia, 2 cases of headache and 1 case of malaise (0.1%, 0.3% and 0.1% respectively of documented doses). The majority of solicited local or general symptoms were of short duration (4days) and all these adverse events reported resolved without sequelae. There was no significant increase in reactogenicity after subsequent (up to 4) doses. In these studies 4 SAEs have been reported. Of these, only one SAE probably related or suspected of being related to vaccination (elevated ALT) occurred during the trial after dose 2. However in the same study, four cases of elevated ALT were reported as SAEs in the control group (Rabies). There were 3 other reports judged unlikely to be related to vaccination, these were: 1) erectile impotence, 2) hospitalization with jaundice and urinary tract infection 5 months after study completion (6 months after the last dose) died the next day of suspected fulminant hepatitis, 3) pneumonia cirrhosis and hepatocellular carcinoma reported 5 months after dose 3 and died 6 months later. A summary table of the clinical experience with AS02 and AS02A in adults and children is provided below.

| Vaccine / Trial | Location | Number of Participants | Total NumberofVaccinations | Reactogenicity Results |
|---------------------------------|------------|------------------------------------|----------------------------|--|
| | | | in Trial | |
| FMP1/AS02, RTS,S/AS02 or | WRAIR | 60 adults, malaria naïve | 176 | No vaccine related SAEs, 4 severe injection site reactions |
| FMP1+RTS,S/AS02 | | | | (pain), all resolved in 24 hours; no significant |
| | | | | laboratory abnormalities |
| FMP1/AS02 | WRAIR | 15 adults, malaria naïve | 45 | No SAEs or severe reactions; no significant laboratory abnormalities related to vaccination |

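### Symptom-free laboratory adverse events cannot exceed grade 1 under section 10.2, and it is contradictory whether they count as unsolicited events

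*Protocol*

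**What the plan says.** Protocol 10.1.1 defines an adverse event through "physical signs, symptoms and/or laboratory detected changes occurring in any phase of the clinical study". After setting aside the solicited list of 10.1.4, it adds: "All other adverse events will be recorded as unsolicited adverse events". Section 10.1.3 agrees on who may find an event: "the investigator will evaluate all adverse events either observed by the investigators or reported by the participant spontaneously or in response to a direct question".

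Section 10.1.5 is narrower: "Unsolicited adverse events are adverse events reported by the participants that are different from those solicited" (or solicited symptoms that start after the 8-day period). The glossary entry for unsolicited symptoms also describes what participants mention, and the co-primary endpoint in 12.1 is worded in terms of unsolicited symptoms.

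On grading, Table 3 covers only the solicited local and general events. For the rest, 10.2 says: "For all other adverse events than those in Table 3, maximum intensity will be assigned to one of the following categories". Grade 1 is "An adverse event which is easily tolerated by the subject, causing minimal discomfort and not interfering with everyday activities". Grade 2 requires interference with everyday activities and grade 3 requires that they be prevented. Grade 0 means that there is no adverse event.

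Sections 14.4 and 14.5.2 require the SMC and DSMB to be told of SAEs and of grade 3 events, with grade 3 taken from Table 3, section 10.2. Section 12.5.3 assesses the intensity of unsolicited symptoms. In a separate laboratory paragraph it tabulates abnormal values judged clinically relevant, and it compares hemoglobin, creatinine and ALT over 12 months.

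**The concern.** Two stated rules do not fit the kind of event that the laboratory schedule is there to find.

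First, a raised ALT or creatinine, or a fall in a blood count, often produces no symptom. A scale built on discomfort and activity has no way to express its size. The intensity summary would then show a small and a very large silent change alike as grade 1, and the grade 3 notice would not respond to either.

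Secondly, whether such an event belongs to a co-primary endpoint depends on which section the person completing the CRF follows.

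The matter is not remote for this product. Section 4.3.1 reports that in the Gambian RTS,S/AS02 studies the one SAE considered probably or possibly related to vaccination was a raised ALT, and that four raised ALTs in the rabies control group of the same study were also reported as SAEs. With 20 per arm, one participant moved in or out of the count changes an arm's proportion by 1/20 = 5 percentage points.

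**Working it through.** **The plan's own figure.** Table 4 gives the chance of at least one event among 20 vaccinees as 1 − (1 − p)^20.

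| True rate p | Calculated | Stated |
|---|---|---|
| 0.01 | 0.182 | 0.18 |
| 0.05 | 0.642 | 0.64 |
| 0.08 | 0.811 | 0.81 |
| 0.10 | 0.878 | 0.88 |

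The table is right. The problem lies in the definitions.

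**Grading.**

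1. A laboratory-detected change is an adverse event (10.1.1).
2. Table 3 has rows for pain, swelling, erythema, arm motion, fever, chills, nausea, headache, malaise, myalgia and joint pain, and none for a laboratory value.
3. It therefore falls to the general scale of 10.2.
4. Without symptoms it does not interfere with or prevent activity, so grades 2 and 3 cannot be met. Once accepted as an adverse event it is not grade 0 either. Grade 1 is the only grade left.

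Illustration, with an assumed value: ALT must be below 35 IU/L at entry (6.5). A symptom-free 350 IU/L on Day 74 is more than 350/35 = 10 times the entry value, and grades 1.

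**Notice.** Whether the reference in 14.4 and 14.5.2 is read as Table 3 alone (no laboratory row) or as the whole of 10.2 (grade 1 at most), a silent event that is not an SAE never qualifies.

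**Counting.** The sections compare as follows.

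| Section | Silent laboratory event is unsolicited? |
|---|---|
| 10.1.1 | Yes, by default |
| 10.1.3 | Recorded, since investigator-observed events are included |
| 10.1.5 | No, not reported by the participant |
| Glossary, 12.1 | Worded as symptoms; points to no |

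**Reach.** Panels after dose 1 are due on Days 14, 30, 44, 60, 74, 90, 180, 270 and 364 (8.1 and 7.1.5, taking three-monthly visits from Day 180). The unsolicited windows are the vaccination day plus 30 days. On nominal days they run over Days 0–30, 30–60 and 60–90. Six panel days fall inside: 6 × 40 = 240 panels. These are panels drawn; the protocol gives no rate of silent abnormality.

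**Effect of the counting rule.** Suppose a silent laboratory event has a true rate of 8%, and a share c of such events is recorded as unsolicited. Both are assumptions. The chance that the endpoint shows at least one among 20 is 1 − (1 − 0.08c)^20:

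- c = 1: 0.81
- c = 0.5: 0.56
- c = 0.25: 0.33
- c = 0 (10.1.5 applied strictly): 0

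**The case against.** The strongest reply is that laboratory safety has its own channel. Section 8.1 lists CBC, creatinine and ALT as safety tests. Section 12.5.3 tabulates relevant abnormalities and compares hemoglobin, creatinine and ALT. Section 10.4 follows clinically significant abnormalities until they are normal or explained. The SMC reviews accumulated safety data about three weeks after doses 1 and 2, after the nominal Day 14 and Day 44 draws, and that review is not limited to grade 3 events. A marked rise could also be judged an important medical event, hence an SAE (10.5.1). All of this stands. A reader might infer that laboratory signals would disappear from the safety evaluation; the documents do not support that.

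Nor is exclusion from the endpoint settled. Sections 10.1.1, 10.1.2 and 10.1.3 favour inclusion, and 10.1.5 may simply be loosely worded. That also stands, and it is why this is a contradiction to reconcile.

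A reader might also think that under-grading alters the co-primary result. It does not: that endpoint counts occurrence, and intensity is a further description. Nor do the documents show that comparison with earlier trials would be lost. The first FMP1 study also defined grade III by daily activity (4.3.4), and the earlier raised ALTs are described as SAEs, without a laboratory grade. ALT was not the only laboratory finding either, since 4.3.4 mentions occasional raised CPK.

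Finally, the cut-off for clinically relevant values may properly sit in the Report and Analysis Plan that 14.5.2 and 14.6 foresee. That is fair for the tabulation. It does not answer the point on grading: investigators assign intensity on the CRF during the trial, and the protocol itself fixes the notice by that grade. A later analysis plan can re-tabulate values but cannot supply a notice that was never triggered.

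**Conclusion.** The point holds as a defect in a stated rule and an internal contradiction. Symptom-free laboratory events are capped at grade 1 in the intensity summaries, and non-serious ones cannot trigger the grade 3 notice to the SMC and DSMB. Whether they count in the co-primary unsolicited endpoint depends on the section followed.

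The reach is about 240 panels on nominal visit days. All 9 post-dose panels would give 9 × 40 = 360, but the 120 drawn at Days 180, 270 and 364 lie outside the 31-day windows. The number of events affected cannot be estimated from the protocol; the detection figures above rest on an assumed 8% rate and assumed recording shares. The underlying values remain available and analysed, so what is lost is severity, the automatic notice and a consistent count. The point should be corrected, but it does not undermine the trial.

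**What to change.** - **Definition.** Reconcile 10.1.5, the glossary entry and the endpoint wording in 12.1 with 10.1.1 and 10.1.3, so that events found by the investigator or the laboratory count as unsolicited adverse events.
- **Grading.** Add to 10.2 a numeric intensity scale for ALT, creatinine, hemoglobin, WBC, lymphocytes and platelets. The sponsor should choose the bands from the site reference ranges. State that laboratory events are graded on this scale and not on the activity scale.
- **Notice.** Make the grade 3 reference in 14.4 and 14.5.2 point to the laboratory scale as well as to Table 3.

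The cost is protocol wording, one table and a small CRF edit, with no extra blood or visits. The downside is that some symptom-free values will now count as grade 2 or 3, which adds notices to the SMC and DSMB and makes the intensity table look less favourable.
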